Title: STAND ALACRITY CENTER Signature Project: STAND Triaging and Adapting to Level of Care

Lay title: STAND Finding and adapting the level of care

Research study IRB# 22-000635

[figure not shown]
Protocol version: 01/26/2026

Research Description

The STAND ALACRITY CENTER Signature Project: STAND Triaging and Adapting to Level of Care study is a randomized controlled trial comparing 2 approaches for treatment triaging and adaptation. This study is being conducted among community college students enrolled in the Screening and Treatment for Anxiety and Depression (STAND) initiative at East Los Angeles College (ELAC). 1,000 students who meet study eligibility criteria will be enrolled over 5 years. Participants will be randomized to receive care under 1 of 2 models: symptom severity-based decision making (SSD) or data-driven decision making (DDD). Participation involves completing online self-report assessments in addition to engaging in an assigned depression or anxiety service as provided by this study. See **Figure 1** for general overview of the research design.

This study is funded by the National Institute of Health – National Institute of Mental Health. This research study is conducted by [name], from the Departments of Psychology and Psychiatry, and [name], from the Department of Psychiatry, at UCLA. This study is affiliated with the UCLA Depression Grand Challenge.

Figure 1

Sample

This study aims to enroll approximately 200 participants per year, for a total sample size of 1,000 participants over five years. To reach this sample size, we expect to consent up to 5,000 students.

Eligibility

Interested individuals are directed to the study webpage to learn about STAND at ELAC, and create an online account. Initial study eligibility is assessed through self-report questions administered during the account creation process. All individuals are informed during screening that they are welcome to sign up for the free virtual wellness program Stand For All, without participating in this research study. If an individual is deemed ineligible at any point during screening, they are notified and offered alternative resources, including Stand For All.

Inclusion criteria:

- Age 18 – 40 years
- Competent to understand informed consent and express willingness to follow study procedures.
- Currently enrolled ELAC student
- Either uninsured or on California Medicaid (Medi-Cal).
- Proficient in English
- Have private access to internet

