Study participation is completely remote and lasts 40 weeks after initial orientation/intake. Participation requires creating an online account on the STAND at ELAC study website in order

to complete eligibility screening. Once initial eligibility is confirmed, those who choose to participate must sign an online consent form and complete baseline assessments. Upon completion of baseline assessments, participants are randomized to 1 of 2 treatment conditions (SSD or DDD), and assigned to a level of care based on their responses to baseline surveys. Participants must attend a remote orientation or intake session for their assigned level of care, and thereafter are asked to complete weekly online surveys over the course of 40 weeks. Participants are considered enrolled after completing consent, baseline assessments, and attending an orientation/intake session for their assigned level of care.

Condition Assignment

Participants in this study will be randomized into one of two conditions which are differentiated by approach for decision making in treatment triage and treatment adaptation. The standard approach used in previous STAND studies is **symptom severity-based decision making (SSD)**. SSD participants will be triaged and adapted to level of care based on reported symptom severity only.

The experimental approach is **data-driven decision making (DDD)**. DDD participants will be triaged and adapted to a level of care using a multivariate predictive algorithm that is iteratively updated annually. This algorithm determines level of care based on individual participant characteristics, coupled with reported symptom severity. The DDD *triaging* algorithm will be implemented beginning in Year 1 of this project and the DDD *adaptation* algorithm will be implemented beginning in Year 2.

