In **SSD adaptation**, scores on these CAT scales will determine whether participants move to a different level of care following their week 16 assessment: if participants who began in Tier I show mild to moderate depression or mild to severe anxiety without suicidality, they will be moved to Tier II, or if they show severe depression or suicidality, they will be moved to Tier III. Similarly, if participants who began in Tier II show severe depression or suicidality, they will be moved to Tier III. If a participant skips this assessment, the latest available CAT-MH scores are used.

In **DDD, triaging** will be determined by symptom scores from the CAT-MH in conjunction with variables from four overlapping, mutually reinforcing clusters. These clusters are: (1) social determinants of mental health, (2) early life adversity/stress, (3) predisposing, enabling and need influences upon health services use, (4) comprehensive mental health status. These clusters were selected based on available empirical evidence and theory. Statistical models that bridge the gap between traditional statistical models and machine learning models will be used for identify the minimum needed variables for these models. Data from prior STAND studies and implementations will inform the specific set of variables used for DDD during Year 1 of the present study. In subsequent years (Years 2-5), the algorithm will be updated and refined annually to optimize the predictive accuracy and utility of the decision-making tool.

The **DDD adaptation** algorithm will be put into practice in Year 2 of this study. During Year 1, all participants will receive SSD adaptation, while statistical models are used to develop DDD adaptation algorithm using the data from Year 1 of the present study, combined with data from prior STAND studies and implementations. In the DDD condition, participants in year 2 of the study are evaluated for treatment adaptation every 4 weeks. Participants in years 3-5 are evaluated for treatment adaptation every 8 weeks based on the output of the DDD adaptation algorithm, which will use data from the latest available CAT-MH scores and other relevant variables from the latest completed self-report measures.

Levels of Care

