Beginning July 8, 2025, participants in the ALACRITY Signature protocol that are initially assigned to Tier 2 or Tier 3 (in both SSD and DDD conditions) will additionally be randomized to one of two

conditions to examine the effect of a technology-enhanced suicide prevention intervention (TE-SPI) on suicide and self-harm risk. The two conditions will be:

- I. **Usual risk management (URM)** is the current standard of care in the project where participants receive outreach from ProtoCall Services and the study team after endorsing suicidal ideation in the weekly surveys.
- II. **URM + TE-SPI** adds a technology-enhanced suicide prevention intervention to the URM. The TE-SPI involves “caring contacts” messages sent to participants, and the use the eTUDES BRITE phone app, which provides users with a tailored coping plan, coping exercises to try in the moment, and a mood thermometer to log daily moods.

Aims

Specific Aim 1:

Triaging level of care - Evaluate whether data-driven algorithms for triaging to level of care lead to greater treatment adherence and outcomes than symptom severity triaging (Years 1-5). Hypothesis a: DDD will show greater adherence (session/lesson completion), greater improvements in depression and anxiety symptoms, and greater improvement in social, occupational and family functioning compared to SSD at 8 weeks. Hypothesis b: between-group differences will increase annually with refinements to DDD algorithms.

Analysis:

- Triaging Algorithm Development - The models we will explore bridge the gap between traditional statistical models and machine learning models which identify a subset of predictors that form a model that accurately predicts week 8 outcomes. This leads to approaches such as regularized regression models, including ridge regression, lasso regression, and elastic net regression that will allow us to identify a smaller and more manageable fixed set of baseline predictors that preserve the predictive accuracy enjoyed by the total set of predictors. At the end of each year, variables included in the predictive modeling will be reviewed for trimming or addition of new variables to be included.

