outcome) from baseline data, current tier and weeks 1-12 outcomes, we will use the model-based estimates for the fixed-effects (baseline and current tier), and the empirical Bayes estimates (see Hedeker and Gibbons, 2006189) for the random effects that describe the trajectory of the outcome based on the repeated assessments through 12 weeks. These fixed and random coefficient estimates will then be used to predict the distal endpoint (16 weeks) and based on this estimated outcome, treatment adaptation will be performed. Model selection will be based on minimizing the root mean square error (RMSE) between the actual observed 8-week outcomes and the estimated outcomes. Once calibrated, we will use this predictive model to set thresholds on what level of change or lack thereof will lead to adaptation of level of care (tier shift) at 4-week intervals of treatment rather than having to wait for several months to evaluate outcomes. The algorithm will be designed such that it will predict the lowest level of care that would produce improvement in symptoms at the outcome point.

Specific Aim 3:

Adapting Level of Care - Evaluate whether data-driven algorithms for adapting level of care lead to greater treatment adherence and outcomes than symptom severity adaptation (Years 2-5). Hypothesis a: Compared to SSD, DDD will show greater treatment adherence (session/lesson completion), greater improvements in depression and anxiety symptoms and social, family and academic functioning at 16 weeks, 24 weeks, 32 weeks, and 40 weeks. Hypothesis b: between-group differences will increase annually with refinements to DDD algorithms.

Analysis:

- Adaptation Outcomes: Outcome analyses will be conducted in three different ways similarly to the analyses planned for the triaging treatment outcomes. Secondary analyses will also be performed. These include 1) using a linear mixed model to explore mediating factors and 2) performing cost-effectiveness analyses of the adaptation algorithm.

Specific Aim 4:

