- Assuming a sample size of n=1000 (500 per group [SSD v. DDD], a drop-out rate of 5% between assessment periods, a Type 1 error rate of 5% for a one-sided test, power of 80%, a linearly increasing effect size (difference between SSD and DDD groups), outcomes will be assessed for Aim 3 at week 16, week 24, week 32, and week 40, and first order autocorrelation of rho=0.3, we will be able to detect a linearly increasing effect size culminating in 0.26 standard deviation unit difference between SSD and DDD groups. Note that these are linearly increasing effect sizes over time with trends that end at these levels of separation, so even smaller differences earlier in time, that increase in magnitude over time, are captured by these analyses with adequate statistical power.

Specific Aim 5:

Recruitment Uptake - Multiple strategies to improve recruitment will be tested throughout the study lifetime.

During Years 2 - 3, the standard advertisement campaign for STAND (that was delivered in Year 1) will be supplemented with community informed video testimonials to facilitate indirect social contact with students who have lived experiences of depression and anxiety. The content of the social contact videos will be informed by extant research on help-seeking interventions and findings from focus groups; selected testimonials will be those that present potentially important themes (stigma, benefits of treatment, treatment hesitancy, etc.). The utility of the videos will be assessed by comparing screening rates across selected years of the project.

Community input via focus groups (conducted through IRB-22-0220) will guide potential adaptations to the videos and engagement interventions for Years 3 and 4.

Analysis:

- Analyses will be primarily descriptive and will include chi-square tests to compare screening rates during Year A when recruitment did not use video testimonials with Year B, when video testimonials were used.

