- **10/30/2024** – Inclusion of video testimonials in recruitment materials, addition of pilot interventions to increase uptake of STAND (text messaging around barriers and informative animation). Editorial overhaul to protocol and consent form to provide clarity around research procedures. Updated consent form.
- **8/28/2025** – Addition of Aim 5 - Recruitment Uptake including video testimonials, updated recruitment documents to reflect rebranding from "The STAND at ELAC Research Program" back to "STAND at ELAC." Updated consent form.
- **7/17/2024** – Compensation increased from \$475 to \$490 and US Bank compensation discontinued, e-gift cards exclusively used to pay compensation. Updated consent form
- **6/5/2024** participants given choice to receive compensation through either e-gift-cards or US Bank, removed enrollment cap of 200 participants/year. Updated consent form
- **12/15/2023** - Compensation increased from \$275 to \$475. Addition of raffles to recruitment strategies. Updated consent form.

STAND at ELAC Consent Form

UNIVERSITY OF CALIFORNIA LOS ANGELES CONSENT TO PARTICIPATE IN RESEARCH

Research Study Name: STAND Finding and adapting the level of care

Thank you for your interest in STAND at ELAC! This study is funded with a grant from the National Institute of Mental Health (NIMH) and is being conducted under the UCLA Depression Grand Challenge by [name] (from the Department of Psychology and the Department of Psychiatry and Biobehavioral Sciences) and [name] (from the Department of Psychiatry and Biobehavioral Sciences), at the University of California, Los Angeles (UCLA).

WHAT SHOULD I KNOW ABOUT A RESEARCH STUDY?

- Research studies are voluntary. Whether or not you take part is up to you.
- Someone will explain this research study to you.
- You can discuss this study with friends, family, or your doctor.
- If you have any questions, you can ask the researchers for more information before deciding to participate.
- You can agree to take part and later change your mind.
- Your decision will not be held against you.

WHAT IS THE STUDY RESEARCHING?

The STAND at ELAC research study is evaluating different methods for finding the most appropriate level of care for each student, and adapting that care to meet individual needs.

WHY IS THIS STUDY BEING DONE?

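### Aim 3's power is stated on all 1,000 participants, but the adaptation comparison runs only in Years 2-5, about 800 (400 per group) at the planned rate

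*Protocol*

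**What the plan says.** The power paragraph is the last item under Specific Aim 4, but it names Aim 3, the SSD and DDD groups, and weeks 16, 24, 32 and 40. It starts "Assuming a sample size of n=1000 (500 per group [SSD v. DDD], a drop-out rate of 5% between assessment periods". It adds a one-sided 5% test, 80% power, first-order autocorrelation of 0.3 and a difference that grows linearly over time, and concludes "we will be able to detect a linearly increasing effect size culminating in 0.26 standard deviation unit difference between SSD and DDD groups".

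Other sections fix who can contribute to that comparison:

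- Specific Aim 3 asks whether data-driven adaptation will "lead to greater treatment adherence and outcomes than symptom severity adaptation (Years 2-5").
- Condition Assignment says of the DDD adaptation component that the "algorithm will be implemented beginning in Year 2". Its DDD adaptation paragraph adds: "During Year 1, all participants will receive SSD adaptation".
- Sample: "This study aims to enroll approximately 200 participants per year, for a total sample size of 1,000 participants over five years". The Recruitment section repeats the target of about 200 per year.
- Specific Aim 1, by contrast, asks whether data-driven triage will "lead to greater treatment adherence and outcomes than symptom severity triaging (Years 1-5"). Its analysis section describes the power analysis as essentially the same one.
- The revision history records for June 2024: "removed enrollment cap of 200 participants/year".

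**The concern.** The n in the power paragraph is the five-year total. That is the right base for the triage comparison in Aim 1, which runs in all five years. It is not the right base for Aim 3. In Year 1 both arms follow the same adaptation rule, so those participants carry no contrast in adaptation, and the aim itself leaves that year out. No section gives a sample size for Years 2-5.

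At stake is the only quantified power statement for either SSD-versus-DDD outcome comparison. As printed, the n and the 0.26 SD cannot both be taken at face value for Aim 3, and a reader cannot tell which of the two to correct.

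**Working it through.** **Inputs.** Power paragraph: 500 per group, one-sided 5%, 80% power, autocorrelation 0.3, 5% loss per interval, four visits, final difference 0.26 SD. Sample section: about 200 per year. Specific Aim 3: Years 2-5.

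**Step 1, sample base.** 4 years × 200 = 800, or 400 per group with equal allocation. The paragraph uses 1,000, or 500 per group.

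**Step 2, can 0.26 be reproduced?** The paragraph gives neither the test nor the difference at week 16. As an assumption, take a linear-trend contrast c = (−3, −1, 1, 3) on a difference growing from zero at week 16, d × (0, 1/3, 2/3, 1). Then

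detectable d = (z₀.₉₅ + z₀.₈₀) × √(2 c′Sc / n) / (c′shape),

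where S is the AR(1) matrix with correlation 0.3 between visits, inflated for the participants lost, and n is the number per group.

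- z₀.₉₅ + z₀.₈₀ = 1.645 + 0.842 = 2.486 (from unrounded values), and c′shape = 1 + 7/3 = 3.333.
- With no loss before week 16, c′Sc = 23.21. At n = 500: √(2 × 23.21 / 500) / 3.333 = 0.0914, and 2.486 × 0.0914 = 0.227 SD.
- With two 5% intervals of loss before week 16, c′Sc = 25.72, the standard error is 0.0962, and the result is 0.239 SD.
- A generalised least-squares slope under monotone dropout gives 0.226 to 0.238 SD.

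So the printed inputs give about 0.23-0.24 SD at 500 per group, not 0.26. Other start values change this. If the difference at week 16 is already a quarter of its final size, the same test gives about 0.30 SD at 500 per group. A start of 0.021 to 0.034 SD returns exactly 0.26. The figure is therefore not shown to be wrong; its derivation is undetermined.

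**Step 3, 400 per group, taking 0.26 as right for 500.**

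- Power for 0.26 SD: 2.486 × √(400/500) = 2.224; Φ(2.224 − 1.645) = 0.719.
- Detectable difference: 0.26 × √(500/400) = 0.291 SD with a zero start. If a start of 0.034 is held fixed, only the remaining 0.226 scales: 0.034 + 0.226 × 1.118 = 0.287 SD.

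**Step 4, 400 per group, printed one-sided inputs and zero start.**

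| Loss before week 16 | Detectable difference (contrast / least squares) | Power for 0.26 SD |
|---|---|---|
| none | 0.254 / 0.252 SD | 82% / 82% |
| one interval | 0.261 / 0.259 SD | 80% / 80% |
| two intervals | 0.268 / 0.266 SD | 78% / 79% |

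On this route 0.26 SD is about what 400 per group delivers.

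**Step 5, a smaller Year 1.** Suppose, as an assumption, that only 100 of the 1,000 were enrolled in Year 1 (450 per group). On the basis of step 3, power for 0.26 SD is Φ(2.486 × √0.9 − 1.645) = 0.762, and the detectable difference is 0.26 × √(500/450) = 0.274 SD.

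**The case against.** **The 800 is not firm.** The yearly cap was removed, so Year 1 may hold more or fewer than 200. The protocol also does not say whether Year 1 means an enrolment cohort or a calendar period. With 40 weeks of follow-up, someone enrolled late in Year 1 could reach week 16 after data-driven adaptation went live. This stands: 800 is a planning figure. But while the total stays at 1,000, any participant with no contrast in adaptation leaves fewer than 1,000 for Aim 3.

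**Year 1 could be kept under intention to treat.** Aim 3 itself leaves it out, and keeping it would mix in participants whose arms differ only in triage. A reader might work out that this cuts power to about 63% (0.26 × 0.8 = 0.208; Φ(2.486 × 0.8 − 1.645) = 0.635). That is an extreme case. It takes 0.26 as right for 500 per group, no difference from triage at weeks 16-40 in Year 1, and a constant 0.26 in Years 2-5, whereas Aim 3 expects differences to grow each year.

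**Aim 3 is underpowered.** A reader might infer this from the 72%. The documents do not support it as a flat statement: step 4 gives 78-82% power for the same difference at 400 per group.

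**0.26 came from a two-sided test.** At 500 per group a two-sided 5% test gives 0.254-0.270 SD under the same assumptions. The protocol says one-sided, so this is a numerical match and no more.

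**The test and start value may be in the statistical analysis plan.** Fair, and their absence is not the point. The point is a stated n that the protocol's own design contradicts.

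**Conclusion.** The concern holds as an inconsistency in the sample base: 500 per group is stated for a comparison that about 400 per group will carry. This rests on about 200 per year and a total of 1,000, and it does not depend on any power formula.

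The effect on the 0.26 SD figure is conditional. If it was derived for 500 per group, the detectable difference for Aim 3 is about 0.29 SD and power for 0.26 SD is about 72%. If the printed one-sided inputs and a zero-start trend were used, 0.26 SD belongs to about 400 per group and the printed n is the error. On either reading the paragraph needs correcting. It does not show that 0.26 SD is wrong or that the trial is too small for Aim 3.

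**What to change.** In the power paragraph, give Aim 3's sample size as the Years 2-5 number: about 400 per group, or the number actually enrolled from Year 2. Confirm which inputs produced 0.26 SD, then recompute the detectable difference for that n at the stated one-sided 5% and 80% power. In the Specific Aim 1 analysis section, where the power analysis is described as essentially the same, add that Aim 1 keeps n=1000 (Years 1-5).

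This edits one paragraph and adds one clause. It needs no extra participants, visits or analyses. The cost is a smaller stated n and possibly a slightly less favourable detectable difference for Aim 3.

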During Year 3 of recruitment, we will test two specialized processes designed to increase participant uptake into the STAND program. Upon enrollment, participants will be initially randomized to one of three conditions: (1) Emotion Regulation Uptake, (2) Text Messaging Uptake or (3) STAND as usual. This randomization will occur prior to their randomization into SSD and DDD conditions. The Emotion Regulation and Text Messaging Uptake conditions are designed to test two separate methods to increase the rates that participants schedule and attend a STAND orientation. Hypothesis a: The two recruitment uptake conditions will lead to higher rates of completed orientations. Hypothesis b: The two recruitment uptake conditions will not lead to any differences in the rates of completed orientations.

Analysis:

- To examine whether the two recruitment uptake conditions lead to higher rates of completed orientations, t-tests will be conducted to analyze whether significant differences in the rates of completed orientations are found, compared against the STAND as usual control condition.

Specific Aim 6:

To evaluate a technology-enhanced suicide prevention intervention (TE-SPI) that includes treatment components with demonstrated benefits in prior research (safety planning, BRITE app, caring contacts to support safety plan use, hope, and reasons for living) and leverages mobile technology to deliver just-in-time adaptive interventions when intervention is most needed. Using Tier II and Tier III from the Signature Project, which include students for whom

additional intervention for SU/SU risk is indicated, this work will use a rapid prototyping and testing model to develop and test an adaptation of the existing BRITE app plus safety planning for the ELAC population. We will evaluate the TE-SPI with STAND usual risk management protocol (URM) compared to STAND URM alone. We hypothesize that TE-SPI will a) lead to increased treatment engagement/contacts (i.e. app, STAND); b) demonstrate safety as indicated by low levels of self-harm related adverse events (e.g. hospitalizations, ED visits); c) be associated with fewer SU/SU events and greater improvement in suicidality, compared to URM; and d) that intervention engagement/dose received will lead to reduced SU/SU behavior.

Study Procedures

Recruitment

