Active recruitment will take place during each academic year at ELAC. Promotional activities as outlined above will continue during the rest of the academic year as necessary for maintaining awareness about the study on the college campus. Materials related to these strategies and specific to this research study are uploaded to the online IRB application. Note that in these materials, we have explicitly limited the times we discuss the affiliation of the study with UCLA. Many community college students seek admission to UCLA and might become concerned about disclosing mental health information prior to learning about the confidentiality limits discussed in the informed consent form, and thus not engage with the present research study.

Prospective participants who have provided their contact information will be contacted (via email, phone call or text message) by study staff within 14 business days to review study eligibility and research procedures. Participants in this stage may be guided by staff or automated prompts to continue their enrollment process as needed.

Study enrollment has a target sample of approximately 200 participants per year. Additionally, for this study, we require the following allocation per service across both conditions per year: n = 20 for Wellness, n = 120 for Digital Mental Health + Coaching, n= 60 for Clinical Care. Once the desired sample size per service is reached for the research study, upon review, enrollment may conclude for the academic year and students will be referred out for alternative services if needed. Care may continue to be available through the STAND for All (non-research) program. Participants may be placed on a wait list for the research study in the case that a spot in their recommended care service is expected to become open within a clinically acceptable timeframe.

Consent

Participants sign research consent prior to their assignment to the recommended level of care. This study utilizes the REDCap eConsent framework to collect electronic signatures from

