Caring Contacts Messages: Additionally, participants randomized to URM+TE-SPI, will also receive caring contact messages via text. Participants will be informed that messages will not be monitored on a 24/7 basis. Staff will communicate that these messages are intended for support only and are not a substitute for therapy or comprehensive interventions. If participants respond to caring contacts messaging requesting additional support or resources, staff may direct participants to their personal coping plans or the usual risk and case management procedures will be followed, and staff may provide referrals to community resources.

Figure 2 URM & URM+TE-SPI

Figure 3. Overview of Project 3 Design for RCT (Years 3 - 5) Comparing Technology-Enhanced Suicide Prevention (TE-SPI) to Usual Risk Management (URM).

Abbreviations. URM, Usual Risk Management; TE-SPI, Technology-Enhanced Suicide Prevention; SSD, Symptom-Severity Decision Making; DDD, Data-Driven Decision Making.

Participants who were randomized to URM+TE-SPI will receive 1 additional survey (BRITE Satisfaction & Usability Survey) at weeks 12 and 40, asking them to rate the perceived helpfulness of the intervention components (BRITE app, coping plan, caring contacts). Data on app use and responses to caring contacts will also be stored.

Assessments

Once participants complete enrollment, they are directed to a unique link to complete baseline assessments. Participants are instructed to complete the baseline assessments before they can be assigned to a service, and may receive reminders from staff to complete their baseline assessments. Participants may be asked to re-do baseline surveys if > 4 weeks has passed between baseline completion and initiation of care in their assigned service tier.

Participants will be asked to complete a brief symptom survey (CAT-MH) as part of their baseline assessment and weekly thereafter. Additionally, they will be asked about current stress (1 item), current financial, housing and food insecurity, and perceived social support.

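### Aim 6(b) treats a low absolute level of self-harm events as a demonstration of TE-SPI safety, but such a level cannot show whether TE-SPI adds risk over the randomised URM arm

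*Protocol*

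**What the plan says.** Specific Aim 6 first sets the comparison: "We will evaluate the TE-SPI with STAND usual risk management protocol (URM) compared to STAND URM alone". It then lists four hypotheses. Hypothesis (b) is that TE-SPI will "demonstrate safety as indicated by low levels of self-harm related adverse events", with hospitalizations and emergency department visits as examples. Hypothesis (c) is that it will "be associated with fewer SU/SU events and greater improvement in suicidality, compared to URM". The words that name the comparator belong to (c); clause (b) has none.

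The comparison is randomised and concurrent. The TE-SPI section under Levels of Care states: "Beginning July 8, 2025, participants in the ALACRITY Signature protocol that are initially assigned to Tier 2 or Tier 3", in both decision-making arms, "will additionally be randomized to one of two" conditions, URM or URM + TE-SPI.

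The Recruitment section gives the planned yearly numbers by service: "n = 20 for Wellness, n = 120 for Digital Mental Health + Coaching, n= 60 for Clinical Care". Aim 6 has no analysis paragraph, and the protocol gives it no sample size, self-harm event rate, allocation ratio or significance level.

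**The concern.** Clause (b) names both a conclusion (safety demonstrated) and the evidence that would support it (a low level of events). That evidence does not bear on the question. A low level shows that events were uncommon under TE-SPI. It does not show that they were no more common than they would have been under URM alone. Only the contrast with URM shows that, and the trial already provides it.

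Hypothesis (c) does not fill the gap. It is a hypothesis of benefit, and failing to show fewer events would not exclude more. The events in (c) are also not defined, so their overlap with the adverse events in (b) is unclear.

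At stake is a published statement that an add-on suicide-prevention intervention was shown to be safe, in a population that includes students with severe depression or suicidality, on data that may be compatible with a material excess of self-harm events.

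**Working it through.** The protocol states no figure for this hypothesis, so there is nothing to reproduce. The check asks what the criterion can and cannot detect.

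**Inputs**
- Tier II and III enrolment: 120 + 60 = 180 per year (Recruitment section).
- Allocation: not stated; 1:1 assumed, so 180 / 2 = 90 per arm per year.
- Accrual: one to two years from July 2025, so n = 90 to 180 per arm. The figure caption "Overview of Project 3 Design for RCT (Years 3 - 5" could suggest longer, so n = 270 is shown as a sensitivity case.
- URM risk p of at least one event by week 40: not given; 1%, 2%, 3% and 5% assumed.
- Meaning of *low*: not given; an observed TE-SPI proportion at or below c = 5% or 2% assumed.
- No dropout assumed.

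**1. Chance that a doubled risk still looks low.** With X the number of TE-SPI students with an event, X ~ Binomial(n, 2p), and the criterion is met if X ≤ floor(c × n). For c = 5% the limits are 4 of 90, 9 of 180 and 13 of 270. For c = 2% they are 1 of 90, 3 of 180 and 5 of 270.

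| URM risk → doubled | c = 5%: n = 90 / 180 / 270 | c = 2%: n = 90 / 180 / 270 |
|---|---|---|
| 1% → 2% | 0.97 / >0.99 / >0.99 | 0.46 / 0.51 / 0.55 |
| 2% → 4% | 0.71 / 0.81 / 0.80 | 0.12 / 0.07 / 0.04 |
| 3% → 6% | 0.37 / 0.36 / 0.25 | 0.03 / 0.005 / 0.001 |
| 5% → 10% | 0.05 / 0.01 / 0.001 | 0.001 or less |

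The answer runs from almost always to almost never, depending on two numbers that the protocol does not supply.

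**2. Why no cutoff cures this.** The pass probability depends only on the true TE-SPI risk. With c = 5% and n = 90, a TE-SPI risk of 2% passes with probability 0.97 whether URM risk is 1% (a doubling) or 2% (no effect). The criterion gives the same answer in both cases. It can also fail a harmless intervention: if both arms have a 5% risk, TE-SPI passes the 5% cutoff with probability only 0.53 (n = 90) or 0.59 (n = 180).

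**3. Would a significance test against URM do instead?** Exact power of a two-sided 5% Fisher test to detect a doubling:

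| URM risk → doubled | n = 90 | n = 180 | n = 270 |
|---|---|---|---|
| 1% → 2% | 0.4% | 3.5% | 8% |
| 2% → 4% | 3% | 11% | 20% |
| 3% → 6% | 8% | 20% | 32% |

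At 90 to 180 per arm, a true doubling would be missed 80% of the time or more, so non-significance is not evidence of safety.

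**4. What the data could support.** Exact (Clopper-Pearson) two-sided 95% upper limits for the TE-SPI risk: 2 events in 90 gives 7.8%; 3 events in 180 gives 4.8%. For the between-arm difference with equal observed rates of about 1% to 3%, the Newcombe 95% interval has a half-width of 5.0 to 6.4 percentage points at 90 per arm and 3.0 to 3.9 at 180 per arm.

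**The case against.** The strongest reply has four parts.

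- *The aim as a whole is comparative.* This stands as a limit on the point. The opening sentence of the hypotheses names URM alone as the comparator, the URM arm is randomised, and (c) compares events with it. A reader might infer that the plan makes no comparison with URM at all; the protocol does not support that. The absence is confined to clause (b).
- *The effect of the weakness cannot be sized from the protocol.* This also stands. A reader might infer that a doubling of risk would usually be declared safe. That holds for some assumed rates and cutoffs and reverses for others: with a 5% cutoff, a doubling from 3% to 6% passes only about 36% of the time. Nor does the protocol say that these events are rare; Tier III, with 60 of the 180 planned places, takes students with severe depression or suicidality.
- *A threshold, margin and safety tables belong in a statistical analysis plan that is not shown.* This is partly right: a number for *low* could sit there. But the protocol itself chooses an absolute level as the indicator of safety, and putting a number on that level would not make it a measure of excess risk.
- *A margin adds little when the interval is so wide.* This is fair. At 3 to 6 points either side, a tight margin is unlikely to be met, so the margin is optional and the interval is the essential part.

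**Conclusion.** The point holds for clause (b). The protocol commits to an unquantified absolute level, without comparator or upper bound, as its demonstration of safety, and such a level cannot show that TE-SPI leaves risk unchanged. This conclusion needs no assumed event rate.

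The size of the problem does rest on assumptions: 1:1 allocation, 90 to 180 per arm, no dropout, and assumed URM risks and cutoffs. With a 5% cutoff, the chance that a doubling passes ranges from above 0.99 (URM risk 1%) to 0.05 or less (5%). With a 2% cutoff it is about 0.5 at 1% and 0.12 to 0.07 at 2%. Actual numbers may differ, because the revision history records that the yearly enrolment cap was removed. The wording of (b) should be changed; the design need not be.

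**What to change.** Drop the claim that safety is demonstrated by a low level of events. In its place, state that in all students randomised to URM or URM + TE-SPI the trial will estimate the difference (URM + TE-SPI minus URM) in the proportion with at least one self-harm related adverse event by week 40, with its 95% confidence interval. Report event counts in both arms and the largest excess that the interval does not exclude. Describe (b) as a safety estimate. Claim that a meaningful excess has been ruled out only if the upper limit lies below a margin that the investigators fixed before looking at outcomes by arm.

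The cost is the rewording of one hypothesis and one additional two-arm estimate, with no added participants or procedures. The downside is a weaker claim: under assumed risks of 1% to 3% the interval is likely to be about ±3 to 6 percentage points, so the probable result is an upper bound on excess risk and not a statement that TE-SPI is safe.
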